### **Study Procedures**

Patients undergoing open ventral hernia repair for clean-contaminated and contaminated abdominal wall hernias meeting inclusion criteria will be randomized to receive a synthetic mesh or a biologic mesh. Randomization will be carried out using computer-generated randomization blocks at the time of enrollment. Stratified randomization will be used with the strata formulated by medical center then by clean-contaminated or contaminated surgical site class. The Investigator will be blinded to patient randomization assignment until the point of intra-operative device use following final CDC wound classification, whereas patients and co-investigators responsible for data analysis will remain blinded to patient randomization until the conclusion of the study period. As such, a double-blinded study protocol will be maintained. Patients randomized to synthetic mesh will receive Soft Mesh™ (CR Bard™, Murray Hill, NJ), and those patients randomized to biologic mesh will receive Strattice™ (LifeCell™, Branchburg NJ). The use of biologic and synthetic meshes in clean-contaminated and contaminated fields is considered experimental; however, the

selection of these prosthetics was based on a careful review of the multiple animal models, preclinical data, and our own clinical experience with each of these materials placed in both clean and contaminated abdominal wall reconstructions.[26, 30-35]

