Upon enrollment into the study, patients will be randomized to either synthetic or biologic mesh for their repair. All patients will undergo our standard pre-operative evaluation. Briefly, it will include a complete set of laboratory studies including complete blood count, comprehensive metabolic panel, albumin, prealbumin, HbA1C (for diabetic patients), and urinalysis. Pregnancy test will be performed for those patients of child bearing potential. Photos may be taken of the anterior abdominal wall. An abdominal pelvic CT scan will be obtained preoperatively in all patients based on our standard approach, (abdominal pelvic CT scan within the past twelve months is sufficient) and any issues postoperatively (including suspected recurrence) will be evaluated with a

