CT scan as clinically indicated. Preoperative demographics and clinical data including sex, race, age, body mass index (BMI), location of the hernia, length and width of the hernia defect, wound classification(per CDC guidelines, table 1), smoking status (active within 3 month of surgery), medical history, surgical history of prior abdominal surgical procedures and prior ventral/incisional hernia repairs will be documented. Intraoperative details will include patient ASA score, patient temperature, use of epidural catheters, size of fascial defect (measured as maximal width and length), fascial layers released (external oblique, posterior rectus sheath, or transversus abdominis muscle), adhesions, concomitant procedures, wound characterization, mesh type, mesh placement, operative time, estimated blood loss, blood transfusion requirement, perioperative antibiotic administration (including type, dose, frequency, and times of initiation and discontinuation), and intraoperative fluid administration. Postoperatively, patients will be evaluated for signs and symptoms of complications along with presence or absence of surgical site infections (SSIs) per CDC definitions as categorized below (Appendix 4), presence or absence of surgical site occurrences (SSOs) and any procedural interventions required to treat these SSOs, presence or absence of hernia recurrence and any reoperations, length of hospital stay, discharge date, time to return of bowel function and any readmission. Wound erythema treated with antibiotics will be considered a wound cellulitis. Wounds that are opened and cultured will be appropriately categorized as postoperative SSIs based on CDC definitions. Type, dose, frequency, and duration of antibiotics will be recorded. Patients will also fill out HerQLes (Appendix 1) and

EQ-5D (Appendix 2) quality of life tools preoperatively and during each post-operative visit, at 4 weeks (± 2 weeks), 6 months (± 2 month), 12 months (± 3 months), and 24 months (± 4 months). See Appendix 7 for Plan for Continuation of Study Follow-up Visits for Patients Previously Enrolled at University Hospital. There is substantial evidence that the majority of hernia recurrences occur within the first 24 months after repair.[5, 15, 41]

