The abdominal wall is reconstructed by initially incising the posterior rectus sheath just lateral to the linea alba. The release is performed at least 5 centimeters above and below the fascial defect. The posterior rectus sheath is then separated off the rectus muscle to the linea semilunaris. If additional release is necessary to achieve fascial closure, the transversus abdominis muscle or the external oblique muscle may be released at the discretion of the surgeon and documented. The posterior components are then reapproximated to exclude the abdominal viscera from the mesh. If the mesh cannot be placed in the retro-rectus or preperitoneal position, then the patient will be excluded from the study. Unless contraindicated due to drug allergies, a pulse lavage antibiotic irrigation using a 3 liter bag with Gentamycin (240 mg), Ancef (3gm), and Bacitracin (50,000 units) will be applied to the posterior rectus sheath and subcutaneous tissues after the components are reapproximated and prior to mesh placement. If there is a drug allergy, then pulse lavage irrigation with sterile saline only will be applied. Final wound classification will occur just prior to mesh placement per CDC criteria. Surgical wounds will be classified based on CDC criteria and only Class 2 and 3 wounds will be included in this study (see Appendix 3):

20

Version date 4/17/19

CCF #7

NCT02451176

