## Class 3- Contaminated

A surgical field with any of the following: open, fresh, accidental wounds; operations with major breaks in sterile technique or gross spillage from the gastrointestinal tract; and incisions in which acute, nonpurulent inflammation is encountered.

Following wound classification, the allocation of the patient to either the biologic mesh cohort or the permanent synthetic mesh cohort will be revealed to the operating surgeon, according to the previously-described computer-generated block randomization scheme stratified by wound classification and medical center. The corresponding prosthetic material will then be placed with at least 5

cm of fascial coverage on all sides of the defect. The mesh will be fixated with trans-abdominal #1 Maxon or PDS sutures at 5-10 cm intervals. Number of sutures to secure the mesh will be documented. All patients will have closed suction drains placed above the mesh and below the fascial closure. These drains will be removed postoperatively when the collected fluid is < 30 cc/day for 48 hours and documented. The fascia will be closed with a running or interrupted Maxon or PDS #1 suture. The skin will be closed loosely with staples. Dry sterile dressings will be placed at the conclusion of the procedure and will be removed on postoperative day 2. No further dressings will be applied to the wound.

Postoperative complications will be defined and recorded on the CRF's based on CDC standardized terms and definitions for Surgical Site Infections as follow: [42, 43]-See appendix 4.

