### *Power Calculation*

33

Version date 4/17/19

CCF #7

NCT02451176

We are investigating two primary outcomes: surgical site occurrences requiring procedural intervention (SSOPI) and hernia recurrence (HR). Surgical site occurrences requiring procedural intervention (SSOPI) is a repeated binary outcome measurement. Hernia recurrence (HR) is a single binary outcome measurement. In a multi-institutional retrospective review of clean-contaminated and contaminated ventral hernia repair, hernia recurrence rates were 29.21% versus 9.01%, and surgical site occurrences requiring procedural intervention were 39.02% versus 9.01% for the biological mesh and permanent synthetic mesh cohorts, respectively.[44] Based on review of these multi-institutional data, an estimated 253 patients will be enrolled in the proposed trial. Assuming a maximum 20% loss to follow-up, 202 patients will remain in the study sample for a 1:1 randomized allocation to each treatment arm (101 subjects per cohort). At the two-tailed overall (two hypotheses) type I error rate of 0.05, the study will have 92% power to detect a significant difference in the rates of hernia recurrence (29.21% vs. 9.01%), and a 100% power to detect a significant difference in surgical site occurrences requiring surgical intervention for the primary hypothesis (39.02% vs. 9.01%; with four repeated measurements and autoregressive correlation of  $\rho=0.5$ ) With 4 centers each performing approximately 1 eligible procedures per week, there will be 192 total procedures performed per year, from which it would be feasible to achieve the total enrollment goal of 253 subjects within 2 years.

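### Randomization is stratified by center and wound class, but no planned model names wound class, the recurrence chi-square and log-rank tests are unstratified, and the reach of the exploratory center terms is unclear

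*Combined protocol and SAP*

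**What the plan says.** **Design.** Study Procedures states: "Stratified randomization will be used with the strata formulated by medical center then by clean-contaminated or contaminated surgical site class". The text after the Class 3 definition describes allocation again as following a "computer-generated block randomization scheme stratified by wound classification and medical center".

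**Analysis.**
- *Primary Analyses of Primary Outcomes*: recurrence gets a plain chi-square test, plus a logistic model for which no covariates are listed. SSOPI gets a generalized mixed model with no stratum terms named. Baseline variables that differ significantly between arms are to be adjusted for. Wound class is among the preoperative data collected ("wound classification(per CDC guidelines, table 1"), so it could enter by this rule.
- *Secondary Analyses of Primary Outcomes*: a two-sided log-rank test without strata. The section holds that an unadjusted comparison is enough in a randomized trial with adequate power. It lists two Cox covariate sets, and neither contains center or wound class. Further covariates may be added afterwards if imbalanced or related to time to recurrence, but the plan ranks such models below the pre-specified ones.
- *Analyses of Secondary Outcomes*: center indicators and treatment-by-center terms will be explored in the regressions. If the interaction is significant, the plan prefers to summarize the treatment effect center by center.

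**Timing.** Study Procedures says "Randomization will be carried out using computer-generated randomization blocks at the time of enrollment" and "Upon enrollment into the study, patients will be randomized to either synthetic or biologic mesh for their repair". It also says "Final wound classification will occur just prior to mesh placement per CDC criteria".

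**The concern.** When randomization balances the arms within strata, an analysis that ignores the strata uses a variance that is too large if those strata predict outcome. The result is not biased toward either mesh, but the test is conservative and gives up some power. Using the design factors costs almost nothing, yet this plan leaves wound class out and leaves center uncertain.

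The rule on significant baseline differences does not fill the gap, because stratified blocks prevent the very imbalance that would trigger it.

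The center paragraph raises a second, conditional question. It can be read as covering every Aim 1 regression or only the secondary outcomes under whose heading it sits. If it reaches recurrence, a chance interaction could move the emphasis from one well-powered overall effect to a set of imprecise center estimates. The plan does not cancel the overall test in that event, but it does not say that the overall effect remains the primary result.

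**Working it through.** **1. The plan's own figure.** Inputs from Power Calculation: recurrence 29.21% vs 9.01%, 101 per arm, overall two-sided 0.05 over two hypotheses. An equal split to 0.025 each is assumed. The plan says: "At the two-tailed overall (two hypotheses) type I error rate of 0.05, the study will have 92% power".

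- Difference = 0.2921 - 0.0901 = 0.2020; mean rate = 0.1911
- Null SE = sqrt(2 × 0.1911 × 0.8089 / 101) = 0.0553
- Alternative SE = sqrt(0.2921 × 0.7079/101 + 0.0901 × 0.9099/101) = 0.0535
- Power = Φ[(0.2020 - 2.241 × 0.0553)/0.0535] = 0.928

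This agrees with 92%, and 202/0.8 gives 253. The calculation is itself unstratified.

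**2. Recurrence: chi-square against CMH.** Simulation at 0.025, 200,000 replicates per scenario. Assumed layout: 4 centers × 2 classes = 8 strata, with 17 class 2 and 8 class 3 patients per arm per center (100 per arm). Stratum effects are on the logit scale, with marginal arm rates held at the plan's values. The documents give no stratum effects for recurrence, so all are assumptions. The 0.708 is borrowed from the infection rates in Significance (8% vs 15%): ln(0.15/0.85) - ln(0.08/0.92) = 0.708. Center effects are evenly spaced over the range shown.

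| Class log-OR | Center range | Chi-square power | CMH power |
|---|---|---|---|
| 0 | 0 | 93.5% | 93.4% |
| 0.708 | 0 | 93.7% | 93.9% |
| 1.0 | 0 | 93.8% | 94.2% |
| 1.4 | 0 | 94.3% | 95.1% |
| 0.708 | ±0.6 | 94.0% | 94.6% |
| 1.0 | ±0.96 | 94.5% | 95.7% |
| 1.4 | ±1.2 | 95.0% | 96.6% |

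Chi-square type I error is 0.025 with non-prognostic strata, 0.023 at class 0.708 alone, and 0.013-0.014 in the last row. CMH stays at 0.024-0.025.

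The result does not depend on the layout:
- Unequal centers (50/25/15/10 per arm): CMH changes power by -0.1 to +1.8 points.
- Five centers: -0.1 to +1.6 points. The plan counts four; five was tried because it also mentions "Patients Previously Enrolled at University Hospital".
- Separate settings (202 patients, 8 equal strata, blocks of 4, 20,000 runs), going from no stratum effect to a class odds ratio of 5 with center SD 1.0: power 93.7% vs 93.6% up to 95.1% vs 96.9%; chi-square type I error from 0.024 down to 0.014.

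**3. Other analyses.**
- Log-rank at 0.05, unstratified vs stratified (10,000 replicates): 96.5% vs 96.5% (not prognostic), 96.7% vs 96.7% (class 0.708), 98.1% vs 99.1% (widest). Unstratified type I error is 0.042 and 0.022 in the last two.
- SSOPI: 100% power either way, by a test on patient means over four visits with AR(1) correlation 0.5. This approximates the planned mixed model and is not that model.
- QOL was not simulated. If the strata explain 2% to 10% of variance, omitting them overstates the SE by a factor of 1/sqrt(0.98) = 1.01 to 1/sqrt(0.90) = 1.05.

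**4. Can the baseline-difference rule bring wound class in?** With 253 patients, 32% class 3 and stratified blocks of 4 or 6, wound class differed significantly between arms in 0 of 3,000 simulated trials. If 20% of patients change class before mesh placement, the figure is 1.7-2.1%.

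**5. The center rule, if applied to recurrence.**
- Per-center power is 47% at 0.05 and 35% at 0.025 with 25 per arm, or 38% and 26% with 20 per arm.
- Half-width of the 95% interval with 25 per arm: 1.96 × sqrt(0.2921 × 0.7079/25 + 0.0901 × 0.9099/25) = 21.1 points, wider than the 20.2-point effect itself. Overall, with 101 per arm, it is 1.96 × 0.0535 = 10.5 points.
- With no true interaction, the chance of a significant 3-df test at 0.05 depends on a test the plan does not name: 0.7% Wald, 4.7% score, 7.6% likelihood ratio.

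**The case against.** The strongest reply is that little is at stake. The unadjusted tests are valid, and the plan gives a reason for choosing them. At the one effect size with any link to the documents (0.708), CMH adds 0.2 points for recurrence, and stratifying the log-rank test adds nothing. SSOPI is unaffected. This stands, and it is why the point is minor.

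The upper end of the range is also generous. The widest case sets an odds ratio of exp(2.4) = 11 between extreme centers on top of exp(1.4) = 4.1 for wound class, so biologic-arm recurrence would run from 6% to 74% across strata. Nothing in the protocol supports that, the operation is standardized, and the plan's list of known recurrence factors contains neither center nor wound class. This too stands: the row is an outer bound, not an expectation.

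Two textual objections carry less weight. The plan does let covariates associated with time to recurrence into the Cox models, and balance would not block that route. But it reaches only the time-to-event models, and the plan itself calls it inferior. The adjusted logistic model lists no covariates, so wound class is unnamed rather than excluded, which still leaves it unspecified. Finally, reading the center paragraph as covering all Aim 1 regressions is reasonable. Even then the chi-square and log-rank tests stay unstratified and wound class stays absent.

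**Conclusion.** The concern holds, at minor severity. The design stratifies on two factors; the analysis names one of them only as an exploratory term of uncertain reach, and the other not at all. The consequence is conservatism, not bias or excess false positives. For recurrence the power difference runs from 0.1 point against CMH to about 1.6 points in its favor in the base layout, and the chi-square type I error lies between 0.025 and 0.013. The stated 92% power and the sample size of 253 are unaffected. These figures rest on assumed stratum effects, an assumed class mix and an equal split of alpha. The point about center-level summaries is conditional on the rule reaching recurrence and on the interaction test being significant.

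**What to change.** First, state which wound class defines the randomization stratum: the class expected at enrollment or the final intra-operative class. The passages quoted above point both ways, and stratified analysis needs one answer. Then:

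- Make the primary recurrence test a single CMH test stratified by center and that wound class, with the chi-square as a sensitivity analysis.
- Stratify the log-rank test in the same way.
- Include center and wound class as fixed terms in the SSOPI, recurrence logistic, Cox and QOL models.
- Say whether the center paragraph covers the primary outcomes. Keep the overall stratified effect as the primary result whatever the interaction test shows, and report center-specific estimates descriptively.

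The cost is SAP wording once the stratum definition is settled. Center is known and wound class is already recorded, so no new data are needed. If the strata prove not to predict recurrence, CMH gives up about 0.1 point of power.

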## Class 2: Clean-Contaminated

Operative wounds in which the respiratory, alimentary, genital\*, or urinary tract are entered under controlled conditions, and without unusual contamination. Specifically, operations involving the biliary tract, appendix, vagina, and oropharynx are included in this category, provided no evidence of infection or major break in technique is encountered.

\*Includes female and male reproductive tracts

## Class 3- Contaminated

A surgical field with any of the following: open, fresh, accidental wounds; operations with major breaks in sterile technique or gross spillage from the gastrointestinal tract; and incisions in which acute, nonpurulent inflammation is encountered.

Following wound classification, the allocation of the patient to either the biologic mesh cohort or the permanent synthetic mesh cohort will be revealed to the operating surgeon, according to the previously-described computer-generated block randomization scheme stratified by wound classification and medical center. The corresponding prosthetic material will then be placed with at least 5

cm of fascial coverage on all sides of the defect. The mesh will be fixated with trans-abdominal #1 Maxon or PDS sutures at 5-10 cm intervals. Number of sutures to secure the mesh will be documented. All patients will have closed suction drains placed above the mesh and below the fascial closure. These drains will be removed postoperatively when the collected fluid is < 30 cc/day for 48 hours and documented. The fascia will be closed with a running or interrupted Maxon or PDS #1 suture. The skin will be closed loosely with staples. Dry sterile dressings will be placed at the conclusion of the procedure and will be removed on postoperative day 2. No further dressings will be applied to the wound.

Postoperative complications will be defined and recorded on the CRF's based on CDC standardized terms and definitions for Surgical Site Infections as follow: [42, 43]-See appendix 4.

### **Superficial Incisional Surgical Site infection (SSI)**

A **superficial incisional SSI** must meet the following criteria:

Infection occurs within 30 days after the operative procedure AND involves only skin and subcutaneous tissue of the incision AND patient has at least ONE of the following:

- a. purulent drainage from the superficial incision.
- b. organisms isolated from an aseptically-obtained culture of fluid or tissue from the superficial incision.

c. superficial incision that is deliberately opened by a surgeon and is culture-positive or not cultured AND the patient has at least one of the following signs or symptoms: pain or tenderness, localized swelling, redness, or heat. A culture-negative finding does not meet this criterion.

d. diagnosis of superficial incisional SSI by the surgeon or attending physician.

NOTE:

a. Do NOT report stitch abscess (minimal inflammation and discharge confined to suture penetration site) as an infection.

b. Do NOT report a localized stab wound or pin site infection. Instead, report these as skin or soft tissue infections, depending on their depth.

c. "Cellulitis" by itself does NOT meet criteria for superficial incisional SSI

d. If infection involves or extends into the fascial and muscle layers report as a deep incisional SSI.

### **Deep Incisional SSI**

A **deep incisional SSI** must meet the following criteria:

Infection occurs within 30 or 90 days after the operative procedure AND the infection involves deep soft tissues (e.g., fascial and muscle layers) of the incision AND patient has at least ONE of the following:

- a. purulent drainage from the deep incision but not from the organ/space component of the surgical site
- b. a deep incision spontaneously dehisces or is deliberately opened by a surgeon AND is culture-positive or not cultured AND the patient has at least one of the following signs or symptoms: fever ( $>38^{\circ}\text{C}$ ), or localized pain, or tenderness. A culture-negative finding does not meet this criterion.
- c. an abscess or other evidence of infection involving the deep incision is found on direct examination, during invasive procedure, or by histopathologic examination or imaging test.
- d. diagnosis of a deep incisional SSI by a surgeon or attending physician.

**NOTE:**

- a. Classify an infection that involves both superficial and deep incision sites as a deep incisional SSI.
- b. Classify infection that involves superficial incisional, deep incisional, and organ/space sites as deep incisional SSI. This is considered a complication of the incision.

**Organ/Space SSI**

An **organ/space SSI** must meet the following criteria:

Infection occurs within 30 or 90 days after the operative procedure AND infection involves any part of the body, excluding the skin incision, fascia, or muscle layers

24

Version date 4/17/19

CCF #7

NCT02451176

that is opened or manipulated during the operative procedure AND the patient has at least ONE of the following:

- a. purulent drainage from a drain that is placed into the organ/space
- b. organisms isolated from an aseptically obtained culture of fluid or tissue in the organ/space
- c. an abscess or other evidence of infection involving the organ/space that is found on direct examination, during invasive procedure,, or by histopathologic examination or imaging test.
- d. diagnosis of an organ/space SSI by a surgeon or attending physician and meets at least one criterion for a specific organ/space infection site listed in NHSN.

All study co-investigators agree to follow these CDC definitions of SSIs for study subjects enrolled in this trial to maximize objectivity of this study measure.

